## **8.2 Adverse Events**

Adverse events (AEs) will be summarized for each randomization arm by body system and preferred term using MedDRA. The adverse events include events of interest, serious and unexpected events, and events which are related to ivabradine use in the opinion of site investigators. The summaries will show participant level and event level counts. Events will be sorted alphabetically by body systems and preferred terms. A data listing of adverse events will be presented.

## **9 ENDPOINT ANALYSES**

### **9.1 Primary Analysis**

The primary analysis will be performed on an intention-to-treat (ITT) basis including all randomized participants. Participant who are not assessed at the 180 day visit due to death or other reasons of early termination, and otherwise medication data not being collected will be coded as failures (ivabradine use=0). The primary analysis will be based on the imputed data. For sensitivity analysis, observed ivabradine use will be used. Given that death is a competing risk of ivabradine use, a competing risk analysis will be performed (see section 11).

The primary analysis will be performed with a logistic regression model, with ivabradine use at 180 days as the binary outcome variable and indicator variables for treatment group main effects

---

 Ivabradine use will be determined from the Ivabradine use pane and will be coded as a “0/1” (no/yes) variable.

and category (0/1) of baseline beta-blocker (BB) use. The treatment effect for the ivabradine at discharge group will be summarized by the odds ratio and associated 95% confidence interval.

Ivabradine use in the ivabradine arm at 180 days is expected to be higher than in the usual care arm.

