## 1 INTRODUCTION

### 1.1 Background

Heart failure is a major public health issue. More than 5 million Americans have HF and the prevalence is expected to increase as the population ages and survival from coronary, hypertensive, and valvular heart disease improves. Data from randomized clinical trials have established the efficacy of a number of medical and device therapies for patients with chronic HFrEF, but patient outcomes remain poor, especially after a hospitalization for heart failure. The 1-year mortality rate after a HF hospitalization is 20-30%, and this number has been relatively unchanged over the past decade. ***These data suggest that there is an unmet need for novel treatment strategies and supports the assessment of new approaches in the post-acute HF setting.***

There is also wide variation in the implementation of clinical trial evidence into routine practice. Previous data highlight a multi-year gap between the generation of new evidence through clinical trials and the adoption of the data into routine clinical practice. This gap in care translates into many unnecessary deaths and hospitalizations each year for patients with HFrEF. While there are multiple reasons for this quality gap, clinical inertia has most often been noted as a major barrier. Ivabradine have been approved for use in Europe for several years for patients with symptomatic chronic HFrEF (LVEF  $\leq$ 35%) and a heart rate  $\geq$ 75 bpm on guideline-directed medical therapy (or intolerance/contra-indication to beta-blocker use). Ivabradine was recently approved for use in the United States. However, ***no US data exist regarding the potential adoption of ivabradine into routine clinical care.***

Since ivabradine is a newly approved drug, this study also serves as a strategy trial to challenge study sites to explore drug acquisition for a drug that has been proven efficacious to the heart failure population and has been added to 2016 ACC/AHA/HFSA guidelines, however, has not been adopted rapidly into clinical practice. Ivabradine is not being provided for this study. Data are being captured to assess the number of subjects

PRIME-HF

who were able to obtain ivabradine pre and post discharge as well as the barriers to acquisition.

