### **10.2 Sample Size Justification**

We assumed that 35% of participants randomized to the usual care arm will be treated with ivabradine at 180 days, and the pre-discharge initiation of ivabradine would increase the use at 180 days to 50%. The usual care event rate is based on investigator estimates of clinical use in the first year following approval by the Food and Drug Administration. At a two-sided Type I error rate of 0.05, 450 participants would provide 85% power to detect a significant difference in the rate of ivabradine use between groups. This sample size estimate is based on a two-group continuity corrected chi-square test and assumes a 1:1 allocation ratio between the pre-discharge initiation of ivabradine and usual care groups. This sample size estimate allows for 8% missing primary endpoint data.

For the KCCQ overall summary endpoint we have made a conservative assumption of 16 points for the standard deviation. For this measure, the medium and large clinically meaningful differences are 5 and 10 points for the KCCQ overall summary measure, respectively. Allowing for approximately 8% missing data, the proposed sample size of 450 participants provides approximately 90% power to detect a difference of 5 points

---

(medium clinically meaningful difference). The power calculations are based on the two sample t-test with a two-sided Type I error rate of 0.05.

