### Data Sources for Endpoints

#### 1. Ivabradine use

a) Ivabradine use (1/0) at 180 days comes from either the current medications data (CM) or the ivabradine usage data (DRG).

If CM.CMIVA=1 and VISITID=50 or DRG.DRIVA=1 and VISITID=50. If missing then it is imputed to 0. (Note: analysis will also be done without imputation).

b) Ivabradine dose change from baseline to 180 days

Ivabradine use and dose at baseline comes from the ivabradine initiation in hospital (EXH) data EXH.EXRECH (use) and EXH.EXLDH (dose) EXH.EXRECH (use) and EXH.EXLDH (dose) (VISITID=10) and ivabradine obtaining the first time (outpatient) (EX) EX.EXREC and EX.EXPDOS (VISITID=60 study wide to be merged in)

For other time points use the ivabradine usage data DRG.DRIVA (use) DRG.DRDSG (dose). Missing doses will be imputed to 0. (Note: analysis will also be done without imputation).

Dose change from baseline to 180 days = EXH.EXLDH, EX.EXDOS (VISITID=10)-DRG.DRDSG (where VISITID=50)

c) Proportion with any initiation

If participant received ivabradine at any time during the visits

If EXH.EXRECH=1 or EX.EXREC=1 or CM.CMIVA=1 or DRG.DRIVA=1 at any visit then ANYIVA=1 else ANYIVA=0; (Note: No imputation of missing ivabradine use occurs for this derivation)

d) Proportion on maximum dose at 180 days

Use ivabradine usage data

If DRG.DRSG =15 (mg) and VISITID=50 then on ivabradine maximum dose=1; else if DRG.DRSG not missing on ivabradine maximum dose=0.

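### The sensitivity analysis for the primary endpoint drops deaths together with unknown outcomes, so it does not isolate the effect of missing data

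*SAP*

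**What the plan says.** SAP 9.1 sets the primary rule. It covers "Participant who are not assessed at the 180 day visit due to death or other reasons of early termination", together with anyone whose medication data were not collected, and codes all of them as ivabradine use = 0. It then gives the check: "For sensitivity analysis, observed ivabradine use will be used".

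Appendix 1, item 1(a), carries this out for day-180 use: "If missing then it is imputed to 0. (Note: analysis will also be done without imputation". It has no separate code for death. SAP 13.2 takes percentages out of non-missing values by default, and a logistic model drops records with no outcome in any case.

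Two other parts of the SAP bear on the point:

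- Section 11 adds a competing-risk analysis in which death is coded separately. Its outcome is time to ivabradine discontinuation, and footnote 12 censors participants who never received a dose at time 0.
- Section 2.4 repeats the primary endpoint in a treated population, defined by receipt of ivabradine at the week 6 visit.

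The protocol gives no rule for deaths in the primary endpoint. Its section 10.2 only allows for 8% missing primary endpoint data.

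**The concern.** The primary rule merges two different groups. A participant who died before day 180 has a known status, which is not taking ivabradine. A living participant with no medication record has an unknown status. The assumption that missing means failure applies only to the second group, so a check on that assumption should vary only the second group.

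As written, the check removes both. It changes the missing-data assumption and also the question, from use among all randomized participants to use among survivors with data. That second step selects on an event after randomization. If the two results differ, the reader cannot tell whether missing data or deaths caused it.

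Neither of the other analyses supplies the missing check. Section 11 does not estimate day-180 use among all randomized participants. The treated-population analysis changes who is analysed, not how missing outcomes are coded.

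**Working it through.** **Inputs from the documents.** Enrolment stopped at 104 (SAP 2.3). Allocation was 1:1 (Protocol 6.2). Planned use was 35% and 50%, with an 8% missing-data allowance (Protocol 10.2). On mortality, Protocol 1.1 says "The 1-year mortality rate after a HF hospitalization is 20-30" percent.

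**Assumptions.** 52 per arm (the split is not given); a constant hazard of death; all counts of users, deaths and losses are illustrative. 18/52 = 34.6% and 26/52 = 50.0% stand in for the planned 35% and 50%.

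**Step 1. The plan's own figure.** The plan states that "450 participants would provide 85% power to detect a significant difference in the rate of ivabradine use between groups". For 35% vs 50%, two-sided 0.05 and 85% power, the continuity-corrected chi-square formula gives 207 per arm, or 414 in total. 414 / 0.92 = 450. The stated sample size reproduces exactly.

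**Step 2. Expected deaths by day 180.** P(dead by day 180) = 1 − (1 − m)^(180/365).

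- m = 0.20: 10.4%, and 0.104 × 52 = 5.4 deaths per arm.
- m = 0.30: 16.1%, and 0.161 × 52 = 8.4 deaths per arm.

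At these rates deaths alone would exceed the 8% allowance.

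**Step 3. What the check changes.** Let U be users at day 180, D deaths without a record, and M living participants with unknown use, in an arm of N. The proportions are:

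- primary coding: U/N
- deaths kept as non-use, M excluded: U/(N − M)
- observed only: U/(N − D − M)

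Take D = 8 vs 5 (ivabradine arm first) and M = 4 per arm (4/52 = 7.7%, close to the 8% allowance). Odds ratios are unadjusted.

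| Users | Primary coding | Deaths kept as non-use | Observed only |
|---|---|---|---|
| 18 vs 18 | 18/52 vs 18/52, OR 1.00 | 18/48 vs 18/48, OR 1.00 | 18/40 vs 18/43, OR 1.14 |
| 26 vs 18 | 26/52 vs 18/52, OR 1.89 | 26/48 vs 18/48, OR 1.97 | 26/40 vs 18/43, OR 2.58 |

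In the second row the total rise is 2.58 − 1.89 = 0.69. Of this, 1.97 − 1.89 = 0.08 comes from the unknown outcomes and 2.58 − 1.97 = 0.61 from dropping the deaths. A reader shown only 1.89 and 2.58 could not see that split.

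An imbalance in deaths is not needed. With 26 vs 18 users, M = 0 and equal deaths, observed-only gives OR 1.99 at 5 per arm and 2.09 at 8 per arm.

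**Step 4. Direction.** Start from 4 deaths and 3 living losses per arm. Observed-only is 26/45 vs 18/45, OR 2.05. Now add 4 deaths in the ivabradine arm.

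| The 4 extra deaths would have been | Observed only | Primary coding | Deaths kept as non-use |
|---|---|---|---|
| all non-users | 26/41 vs 18/45, OR 2.60 | 26/52 vs 18/52, OR 1.89 | 26/49 vs 18/49, OR 1.95 |
| unrelated to use (expected users 41 × 26/45 = 23.7) | 57.8% vs 40.0%, OR 2.05 | 23.7/52 vs 18/52, OR 1.58 | 23.7/49 vs 18/49, OR 1.61 |
| all users | 22/41 vs 18/45, OR 1.74 | 22/52 vs 18/52, OR 1.39 | 22/49 vs 18/49, OR 1.40 |

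The extra deaths can raise, leave unchanged or lower the arm's observed use. In each row the version that keeps deaths as non-use stays close to the primary result, because only the unknown outcomes have been varied.

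**The case against.** The strongest objections, and what remains of each:

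- **The SAP does not ignore death.** The primary analysis counts it as failure, and the sentence after the check in 9.1 points to the competing-risk analysis in section 11. This is true and should be credited. Section 11 still answers a different question, so it does not repair the check.
- **The primary test does not depend on this check.** It keeps all randomized participants, and no decision rule uses the sensitivity result. This stands and limits the weight of the point.
- **A reader could rebuild the needed figure.** SAP 4 reports early dropouts by arm and SAP 10 reports mortality by arm. An approximate, unadjusted version could be assembled, but SAP 10 counts deaths to 194 days and the adjusted model could not be recovered.
- **Some deaths may have an observed value.** SAP 13.1 accepts clinic data within 60 days of the window. This might cover some late deaths; the SAP does not say.
- **The mortality figure may be too high here.** It is a background rate. The trial requires clinical stability and excludes conditions likely to lead to poor non-cardiac survival. This is fair, so 5-8 deaths per arm is an indication and not a forecast.
- **Use among survivors is a legitimate summary.** It is, if labelled as such. It is not a check on the missing-data rule.

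A reader might also infer that the arm with more deaths will always look better. The documents do not support that. It follows only if the number of users is held fixed while deaths vary, which makes every extra death a non-user. Step 4 shows no change when death is unrelated to use, and a fall when users die.

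**Conclusion.** The point holds for the sensitivity analysis in SAP 9.1 and Appendix 1 item 1(a). That analysis drops participants who die without a day-180 record together with living participants whose use is unknown. It therefore conditions on survival and cannot isolate the effect of coding missing as failure, although it is the only stated check on that coding.

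With about 52 per arm the effect can be visible. In the main illustration the odds ratio goes from 1.89 to 2.58, and most of that movement comes from the deaths. These figures rest on assumed counts, an even split and a constant hazard; the documents give no results. No direction of bias can be stated in advance.

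It would also be wrong to conclude that the primary analysis is biased by this or that the SAP overlooks death. The primary analysis is unaffected. This is an inexpensive improvement to a supporting analysis.

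**What to change.** In SAP 9.1 and Appendix 1 item 1(a), redefine the sensitivity analysis of day-180 use:

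- Keep participants who die before the day-180 assessment as use = 0, and exclude only living participants with unknown use. State how a clinic record accepted under the 60-day extension in 13.1 is treated when the participant has died, and apply the same rule in the primary analysis.
- Optionally, add a version that imputes the living unknowns from use at week 6 and at the day-90 call.
- Report, by arm, the number of deaths and the number alive with unknown use.
- Keep any observed-only result as a descriptive summary among survivors.
- Leave the separate coding of death in section 11 as it is.

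The cost is some SAP wording and one additional model run, or more if the optional imputation is added. Death dates and medication use at week 6 and day 90 are already collected. SAP section 1 provides the supplement or amendment route. Addendum 2 refers to database lock and unblinding as past, so a run added after that should be labelled post hoc.

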**Model (logistic):**

**Ivabradine use at 180 days= Intercept+  $\beta_1$ \* treatment +  $\beta_2$ \* baseline beta-blocker use**

**Hypothesis:**

**H0:  $\beta_1=0$**

**H1:  $\beta_1\neq 0$ .**

**The null hypothesis will be rejected if the p-value of the treatment effect is <0.05.**

## **9.2 Secondary Analyses**

### **1. Heart Rate Assessments**

- a. Change in heart rate from baseline to 180 days will be compared across randomization groups. Change will be calculated as follows: (Baseline heart rate – 180 day heart rate). Comparisons across randomization groups will be performed using a linear model with adjustment for baseline heart rate and beta-blocker use. Randomization groups will be included in the regression model as main effect.

---

 Baseline beta-blocker use will be coded as a “0/1” variable with participants who received beta-blocker coded as “1” and those who did not receive beta-blocker as “0”.

 All change from baseline results presented are calculated similarly.

Heart rate is expected to be lower in the ivabradine arm than the usual care arm.  
Thus, change from baseline is expected to be higher in the ivabradine arm.

**Model (linear):**

**Change in Heart Rate (HR) at 180 days = Intercept +  $\beta_1$ \* treatment +  $\beta_2$ \* baseline HR +  $\beta_3$ \*  
baseline BB use**

**Hypothesis:**

**H0:  $\beta_1=0$**

**H1:  $\beta_1\neq 0$ .**

**The null hypothesis will be rejected if the p-value of the treatment effect is <0.05**

- b. Heart rate in bpm at 180 days in the pre-discharge ivabradine group will be compared to the usual care group. Comparisons across randomization groups will be performed using a linear model with adjustment for the baseline heart rate and beta-blocker use. Treatment groups will be included in the regression model as main effects.

**Model (linear):**

**HR at 180 days = Intercept +  $\beta_1$ \*treatment +  $\beta_2$ \* baseline HR +  $\beta_3$ \* baseline BB use**

**Hypothesis:**

**H0:  $\beta_1=0$**

**H1:  $\beta_1\neq 0$ .**

**The null hypothesis will be rejected if the p-value of the treatment effect is <0.05**

- c. The proportion of participants with heart rate < 70 bpm at 180 days will be evaluated. Differences between the randomization arms will be evaluated using the Chi-square test.
2. Changes in symptoms and quality-of-life from baseline to 180 days as assessed by KCCQ and PGA will be evaluated across randomization groups using a linear model with adjustment for the baseline quality-of-life and beta-blocker use. The differences between the randomization arms will be estimated using point estimates and the associated two-sided 95% confidence intervals

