**Change in PGA at 180 days = Intercept +  $\beta_1$ \*treatment +  $\beta_2$ \* baseline PGA +  $\beta_3$ \* baseline**

**BB use**

**Hypothesis:**

**H0:  $\beta_1=0$**

**H1:  $\beta_1\neq 0$ .**

**The null hypothesis will be rejected if the p-value of the treatment effect is <0.05**

Missing values of 180 day heart rate, KCCQ and PGA will be imputed if missing values

---

 If events are rare, p-value from the Fisher's exact test will be reported.

exceed 10% of the observations (see section 12.5).

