### **13.2 General Analysis Conventions/Rules**

All analyzed continuous variables will be summarized using descriptive statistics including number of observations, mean, standard deviation, minimum, 25th percentile, median, 75th percentile, and maximum. All analyzed categorical variables will be summarized using frequency counts and percentages. Percentages are calculated out of non-missing values unless stated otherwise. Comparisons of continuous (or discrete ordered) variables between randomization groups will generally be tested using the Wilcoxon rank sum test. For the secondary endpoint (change from baseline of the measures), analyses will be conducted using the general linear model approach. For comparisons over more than 2 time points, when appropriate, mixed effects models will be used to account for correlation within participant observations and assess time-by-treatment interactions (see Appendix 2 for details). Tests of binomial outcomes between randomization groups will generally be done with a Chi-square statistic. Tests of treatment effects will generally be 2-sided, with type I error = 0.05. Interaction tests will generally be done at the 0.10. Statistical significance is determined at a  $\leq$  0.05 alpha level.

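### The day-180 endpoint of heart rate below 70 bpm is the only primary or secondary endpoint tested without covariates; the test is valid, but it gives up some precision and consistency with its two companion heart-rate analyses

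*SAP*

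**What the plan says.** The proportion with heart rate below 70 bpm at day 180 is listed as a secondary endpoint in the Protocol synopsis, the Protocol executive summary and SAP 2.5.2. Protocol 10.4 gives no method for it, so SAP 9.2 item 1c is the only source: "Differences between the randomization arms will be evaluated using the Chi-square test". The footnote adds: "If events are rare, p-value from the Fisher's exact test will be reported". Neither test takes a covariate.

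The other primary and secondary analyses in SAP 9.1 and 9.2 all do:

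| Endpoint | Method | Covariates besides treatment |
|---|---|---|
| Primary: ivabradine use (binary) | Logistic | Baseline beta-blocker use |
| 1a: change in heart rate | Linear | Baseline heart rate, baseline beta-blocker use |
| 1b: heart rate at day 180 | Linear | Baseline heart rate, baseline beta-blocker use |
| **1c: heart rate below 70 bpm** | **Chi-square or Fisher** | **None** |
| 2: KCCQ, PGA | Linear | Baseline value, baseline beta-blocker use |

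For 1b the SAP writes: "Comparisons across randomization groups will be performed using a linear model with adjustment for the baseline heart rate and beta-blocker use". The only reason offered for 1c is the general convention in SAP 13.2: "Tests of binomial outcomes between randomization groups will generally be done with a Chi-square statistic". The binary primary endpoint already departs from that convention. No adjusted or sensitivity model for 1c appears elsewhere in the documents.

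**The concern.** Protocol 3.2 requires a heart rate of at least 70 bpm at entry, so everyone starts on the same side of the cut-off. Only the continuous baseline value separates a participant who enters just above 70 from one who enters far above it. The plan treats that value as prognostic in 1a and 1b, and then leaves it out when the same day-180 measurement is cut at 70.

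Randomisation is stratified by site only (Protocol 4.4 and 6.2), so nothing in the design balances baseline heart rate. With 104 participants, a chance difference between arms would be corrected in 1a and 1b but not in 1c. The three heart-rate results could then diverge for that reason alone, and whatever precision the covariate offers is left unused.

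**Working it through.** **1. What the plan sizes.** The documents state no power for item 1c. Protocol 10.2 sizes the primary endpoint only, from the assumption that "35% of participants randomized to the usual care arm will be treated with ivabradine at 180 days" against 50% with pre-discharge initiation: "At a two-sided Type I error rate of 0.05, 450 participants would provide 85% power to detect a significant difference". With p0 = 0.35, p1 = 0.50, mean 0.425 and difference 0.15:

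- Uncorrected n per arm = [1.960·√(2·0.425·0.575) + 1.036·√(0.35·0.65 + 0.50·0.50)]² / 0.15² = (1.370 + 0.716)² / 0.0225 ≈ 193.5.
- Continuity-corrected n = (193.5/4)·[1 + √(1 + 4/(193.5·0.15))]² ≈ 206.6, so 207 per arm and 414 in total.
- Allowing for 8% missing: 414/0.92 = 450.

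The plan's figure reproduces. It does not bear on 1c, except that the planned 15-point gap in use is a guide to how far heart rates might differ between arms.

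**2. A plausible arm effect.** If only users' heart rates differ, arm difference = 0.15 × effect per user. An assumed 10 bpm per user gives 1.5 bpm. An arm difference of 6 to 8 bpm would need 6/0.15 = 40 to 8/0.15 = 53 bpm per user. A wider uptake gap than planned would raise the arm difference.

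**3. Power with and without adjustment, N = 104.** Assumptions, none given in the documents: day-180 heart rate mean 76 and SD 12 in usual care; baseline at least 70; 90% on a beta-blocker, with no effect of its own; no missing data; two-sided 0.05. The comparison is Pearson chi-square against the likelihood-ratio test for treatment in a logistic model with baseline heart rate and beta-blocker use. Fits that did not converge count as non-rejections. There were 6,000 runs per setting at 1.5 and 3 bpm and 2,500 at 5 bpm.

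| Arm effect | Correlation | Chi-square | Adjusted |
|---|---|---|---|
| 1.5 bpm | 0.3 | 8.5% | 8.7% |
| 1.5 bpm | 0.5 | 8.3% | 9.6% |
| 1.5 bpm | 0.6 | 8.7% | 9.6% |
| 3 bpm | 0.3 | 17.8% | 17.7% |
| 3 bpm | 0.5 | 18.2% | 20.1% |
| 3 bpm | 0.6 | 18.8% | 21.3% |
| 5 bpm | 0.3 | 41% | 41% |
| 5 bpm | 0.5 | 40% | 44% |
| 5 bpm | 0.7 | 43% | 53% |

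Further runs gave a gain of about 4 points at 6 bpm with correlation 0.5, and none at 0.3. At correlation 0.7 the gain reached about 2 points at 1.5 bpm and about 5 points at 3 bpm. A model with baseline heart rate but no beta-blocker term, with baseline N(80, 10) truncated at 70, gave 59% to 62% at 6 bpm and 83% to 86% at 8 bpm, both at correlation 0.5.

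**4. Type I error.** At 104 and at 414 participants it was 4.5–5.7% for chi-square and 4.7–6.1% adjusted. Both are compatible with 5% given simulation error.

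**5. Size of a chance imbalance.** For baseline N(80, 10) truncated at 70, the SD is 10·√(1 − 0.288 − 0.288²) ≈ 7.9. With 52 per arm, the 95% range of the baseline difference is ±1.96·7.9·√(2/52) ≈ ±3 bpm. At correlation r this moves day-180 heart rate by r·(12/7.9)·3.05 bpm. The density at the cut-off is about 0.0293 per bpm (normal, mean 76, SD 12). The proportion below 70 therefore shifts by about ±4 points at r = 0.3, ±7 at 0.5 and ±10 at 0.7 (unrounded, 9.5).

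For scale, the 95% half-width of the crude difference at 31% versus 47% is 1.96·√(0.31·0.69/52 + 0.47·0.53/52) ≈ 18.5 points. The imbalance shift is a component of that uncertainty, not an addition to it.

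**The case against.** The case for leaving 1c alone has several parts.

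- **The test is valid and follows SAP 13.2.** This stands. A reader might infer that chance imbalance in baseline heart rate biases 1c or inflates its false-positive rate. The documents do not support that: allocation is randomised 1:1, and the error rate of the chi-square already allows for chance imbalance (steps 4 and 5).
- **Baseline heart rate is already used where most of the information lies.** Item 1b analyses the undichotomised measurement with adjustment. In the 5 bpm runs that linear model had 59%, 68% and 84% power at correlations 0.3, 0.5 and 0.7, well above either analysis of the cut variable. The secondary objectives also do not name the 70 bpm cut. This stands, and keeps the point small. It does not explain why 1c alone is unadjusted.
- **The gain may be negligible.** This stands for arm effects near what the planned 50% versus 35% uptake suggests. A reader might infer that adjustment would recover useful power after enrolment stopped at 104. That needs a large arm effect or a high correlation, and the documents give neither.
- **The adjusted model can fail.** With the beta-blocker term, 1–4% of fits at N = 104 did not converge, because few participants are off a beta-blocker under the assumed 90% use. The more than 10% missing day-180 data that SAP 13.5 expects would make this worse. This stands, and calls for a stated fallback.
- **It is late.** SAP Addendum 2 records a decision taken after database lock and unblinding, and SAP section 1 requires an amendment for substantive changes. This stands, and limits what an adjusted result can now claim.

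**Conclusion.** The point holds as a modest one. Item 1c is the only primary or secondary endpoint without covariates, although the two that matter are collected and used in 1a and 1b. The consequence is some lost precision and a possible discrepancy within one family of heart-rate results. It is neither bias nor an invalid test.

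At N = 104, under the assumed values in step 3, the power gain is nil at correlation 0.3. At 0.5 it is about 1 point, 2 at most, for arm effects of 1.5 to 3 bpm, and about 4 points at 5 to 6 bpm. At 0.7 it is larger: about 10 points at 5 bpm. The correlation, the SD and the arm effect are all assumptions, so the range should be quoted rather than any single figure.

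How the missing day-180 heart rates are coded for 1c (SAP Appendix 1, item 2c), and how 25 imputed chi-square results would be combined, are separate questions and do not add to the weight of this one.

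**What to change.** Specify for item 1c a logistic regression of heart rate below 70 bpm on treatment, continuous baseline heart rate and baseline beta-blocker use. Name the fallback if the fit does not converge: penalised likelihood, or dropping the beta-blocker term. Report the odds ratio and a standardised risk difference, each with a 95% confidence interval. Keep the crude proportions and the chi-square beside them.

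The change needs no new data and contradicts no protocol text. It has two small downsides. The odds ratio is conditional on the covariates, which is why the risk difference should accompany it. Some fits will need the fallback. One practical benefit is that a coefficient and its standard error pool directly across the imputations in SAP 13.5.

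For this trial the data are already unblinded. The adjusted analysis should therefore go through the SAP's amendment route, be labelled post hoc and supportive, and not replace the pre-specified chi-square. For a plan still open, it could simply be the specified analysis.
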